## 8.1.3 Definition of Unanticipated Problems (UP)

### **Unanticipated Problems Involving Risk to Subjects or Others**

Any incident, experience, or outcome that meets all of the following criteria:

- Unexpected in nature, severity, or frequency (i.e. not described in study-related documents such as the IRB-approved protocol or consent form, the investigators brochure, etc.)
- Related or possibly related to participation in the research (i.e. possibly related means there is a reasonable possibility that the incident experience, or outcome may have been caused by the procedures involved in the research)
- Suggests that the research places subjects or others at greater risk of harm (including physical, psychological, economic, or social harm).

#### 8.2 Classification of an Adverse Event

## 8.2.1 Severity of Event

considered serious.

For AEs not included in the protocol defined grading system, the following guidelines will be used to describe severity.

- **Mild** Events require minimal or no treatment and do not interfere with the participant's daily activities.
- **Moderate** Events result in a low level of inconvenience or concern with the therapeutic measures. Moderate events may cause some interference with functioning.
- **Severe** Events interrupt a participant's usual daily activity and may require systemic drug therapy or other treatment. Severe events are usually potentially life-threatening or incapacitating.

### 8.2.2 Relationship to Study Intervention

The clinician's assessment of an AE's relationship to study intervention is part of the documentation process, but it is not a factor in determining what is or is not reported in the study. If there is any doubt as to whether a clinical observation is an AE, the event should be reported. All AEs must have their relationship to study intervention assessed. In a clinical trial, the study intervention must always be suspect. To help assess, the following guidelines are used.

- **Related** The AE is known to occur with the study intervention, there is a reasonable possibility that the study intervention caused the AE, or there is a temporal relationship between the study intervention and event. Reasonable possibility means that there is evidence to suggest a causal relationship between the study intervention and the AE.
- Not Related There is not a reasonable possibility that the administration of the study intervention
  caused the event, there is no temporal relationship between the study intervention and event onset, or
  an alternate etiology has been established.

## 8.2.3 Expectedness

Version date: 3/8/2022

PIs and Co-Is at each site will be responsible for determining whether an AE is expected or unexpected. An AE will be considered unexpected if the nature, severity, or frequency of the event is not consistent with the risk information previously described for the study intervention.

# 8.3 Time Period and Frequency for Event Assessment and Follow-Up

The occurrence of an AE or SAE may come to the attention of study personnel during study visits and interviews of a study participant presenting for medical care, or upon review by a study monitor. All AEs including local and systemic reactions not meeting the criteria for SAEs will be captured on the appropriate RF. Information to be collected includes event description, time of onset, clinician's assessment of severity, relationship to study intervention (assessed only by those with the training and authority to make a diagnosis), and time of resolution/stabilization of the event. All AEs occurring while on study must be documented appropriately regardless of relationship. All AEs will be followed to adequate resolution.

Any medical condition that is present at the time that the participant is screened will be considered as baseline and not reported as an AE. However, if the study participant's condition deteriorates at any time during the study, it will be recorded as an AE. UPs will be recorded in the data collection system throughout the study.

Changes in the severity of an AE will be documented to allow an assessment of the duration of the event at each level of severity to be performed. AEs characterized as intermittent require documentation of onset and duration of each episode.

The PI will record all reportable events with start dates occurring any time after informed consent is obtained. SAEs will be followed until resolutions are reached as stated below. AEs will be followed for the duration of an individual's participation in the study. At each study visit, the investigator will inquire about the occurrence of AE/SAEs since the last visit. Events will be followed for outcome information until resolution or stabilization.

All unresolved adverse events should be followed by the investigator until the events are resolved, the subject is lost to follow-up, or the adverse event is otherwise explained. At the last scheduled visit, the investigator should instruct each subject to report any subsequent event(s) that the subject, or the subject's personal physician, believes might reasonably be related to participation in this study. The investigator should notify the study sponsor of any death or adverse event occurring at any time after a subject has discontinued or terminated study participation that may reasonably be related to this study.

# 8.4 Reporting Procedures – Notifying the IRB

It is the investigator's responsibility at each site to report UPs to their IRB in accordance with each site's reporting policies. All UPs at sites other than NYU also need to be reported to the sIRB at NYU Grossman SOM/ NYULH.

## 8.5 Reporting Procedures – Notifying the Study Sponsor

The study clinician will complete a SAE Form within the following timelines:

- All deaths and immediately life-threatening events, whether related or unrelated, will be recorded on the SAE Form and submitted to the DCC/study sponsor within 24 hours of site awareness. See Section 1, Key Roles for contact information.
- Other SAEs regardless of relationship will be submitted to the DCC/study sponsor within 72 hours of site awareness.

All SAEs will be followed until satisfactory resolution or until the site investigator deems the event to be chronic or the adherence to be stable. Other supporting documentation of the event may be requested by the DCC/study sponsor and should be provided as soon as possible.

Version date: 3/8/2022

As a follow-up to the initial report, within the following 48 hours of awareness of the event, the investigator shall provide further information, as applicable, on the unanticipated event or the unanticipated problem in the form of a written narrative. This should include a copy of the completed Unanticipated Problem form, and any other diagnostic information that will assist the understanding of the event. Significant new information on ongoing unanticipated adverse effects shall be provided promptly to the study sponsor.

#### 8.6 Safety Oversight

It is the responsibility of the Principal Investigator and clinician on the study to oversee the safety of the study. Each site's PI and clinician will also provide safety monitoring at their location. This safety monitoring will include careful assessment and appropriate reporting of adverse events as noted above, as well as the construction and implementation of a site data and safety-monitoring plan. Medical monitoring will include a regular assessment of the number and type of serious adverse events.

#### Statistical Considerations 9

#### 9.1 Description of Statistical Methods

Basic descriptive statistics (e.g., means and standard deviations, frequencies and percentages, or medians and interguartile ranges) for variables of interest will be computed. Distributions of each variable will be examined. Graphical approaches will be used to further explore the data where appropriate. Differences in demographics and clinical characteristics at baseline will be evaluated across the three treatment arms. No missing data is anticipated for treatment fidelity or treatment feasibility primary outcomes. For the CSQ-8, missing data will be singly-imputed as the lowest possible score on the CSQ-8, indicating dissatisfaction with the treatment. For clinical utility responder rates, missing data will be singly-imputed as non-response to treatment. For secondary outcome analysis, missing data will be estimated as part of the mixed models procedures. Primary analyses will not be adjusted. Any significant differences on demographic variables between treatment groups will be included as covariates in secondary adjusted models of the secondary analyses described below. SPSS, SAS and R will be used to conduct the analyses. All tests will be two-tailed with alpha set at 0.05.

### Aim 1A. Demonstrate fidelity to MBCT-T and MBCT-V protocols across sites.

Hypothesis (H)1: MBCT-T and MBCT-V sessions (n = 96 sessions) will be administered faithfully [MBCT-TACS scores ≥ 2.5] across treatment arm (MBCT-T vs. MBCT-V) and site (n = 3).

Descriptive statistics (mean and standard deviation) will be calculated for the MBCT-TACS in total (n = 96) and across each treatment arm (MBCT-T, session n = 48 vs. MBCT-V, session n = 48); both treatment arms will be considered administered faithfully if mean MBCT-TACS scores are ≥ 2.5. Descriptive statistics (mean and standard deviation) will be calculated for the MBCT-TACS across each treatment site (NYULH, Einstein, and WFBH n = 32); a site will be considered to have administered the interventions faithfully if mean MBCT-TACS scores are ≥ 2.5.

#### Aim 1B. Demonstrate feasibility and acceptability of MBCT-T, MBCT-V, and EUC.

H1: MBCT-T, MBCT-V, and EUC will be feasible [Primary Outcome: 75% Session Attendance] and acceptable [Primary Outcome: Client Satisfaction Questionnaire-8 (CSQ-8) score > 24] at each site.

Feasibility is assessed using Treatment Session Adherence (n = 144), which will be summed to indicate the number of treatment sessions attended. Descriptive statistics (mean and standard deviation) will be calculated for Treatment Session Adherence across each treatment arm (MBCT-T, MBCT-V, EUC) and each site (NYULH, Montefiore, WFBH). A treatment arm will be considered feasible if on average participants attended 75% of sessions, across all sites. A site will be considered to demonstrate adequate feasibility if on average participants attended 75% of sessions across treatment arms at the site.

Version date: 3/8/2022

Acceptability is assessed using the CSQ-8 at a single time-point. Descriptive statistics (mean and standard deviation) will be calculated for the CSQ-8 across each treatment arm (MBCT-T, MBCT-V, EUC) and each site (NYULH, Montefiore, WFBH). Investigators will endeavor to obtain CSQ-8 scores from all participants; if participants drop out of the study prior to Month 2 and cannot be reached to complete this measure, a total score of 8 will be imputed for these missing data, indicating dissatisfaction with the treatment across all domains. A treatment arm will be considered acceptable if CSQ-8 scores are > 24, across all sites. A site will be considered to demonstrate adequate acceptability if on average participants report CSQ-8 scores > 24 across treatment arms at the site.

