#### B. Demonstrate feasibility and acceptability of MBCT-T, MBCT-V, and EUC.

H1: MBCT-T, MBCT-V, and EUC will be feasible (Primary Outcome: 75% Session Attendance) and acceptable (Primary Outcome: Client Satisfaction Questionnaire-8 (CSQ-8) score > 24) at each site.

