# 7.2.1.3.2 EUC

Participants randomized to EUC will receive usual care and 8 weekly online education modules whose delivery and content are based on control groups from previous behavioral migraine and depression interventions. Modules will be released on a weekly basis, which mirrors the MBCT arms. Participant engagement with each

Version date: 3/8/2022

module happens individually (not in a group) and will be tracked electronically by the secure hosting website. Participants will also complete a daily headache diary.

Table 2. Structure and Content of EUC		
Structure	Weekly Content	
Online module accessed through weblink	1. What is Migraine?	
Multi-tab structure leading	2. Migraine and Depressive Symptoms	

participant through education

Low health literacy definitions

	3. Migraine, Depressive Symptoms and the Brain	
of key concepts	4. Diagnosis of Migraine and Depression	

 
Application of key concepts to the person with migraine and depressive symptoms
 
	5. Treatment Options for Migraine and Depression	
Vignettes depicting people with migraine and depressive	6. Impact of Migraine and Depressive Symptoms	
symptoms demonstrating key concepts	7. Lifestyle Factors for Migraine and Depressive Symptoms	
	8. Communicating with Health Care Providers	

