#### 7.2.1.6 Details of Additional Data Collection by Study Personnel

Name: Recruitment Rate

Type: Primary
Time Frame: Screening/M-1

Brief Description: Recruitment rate assesses study feasibility. Recruitment rate will describe the

proportion of participants who screened positive on the electronic eligibility screener (denominator) and who enroll in the study at the end of the in-person intake visit at

Month -1 (numerator).

Name: MBCT-T Adherence and Competence Scale (MBCT-TACS)

Type: Primary
Time Frame: M2

Brief Description: The MBCT-TACS Adherence Scale assesses treatment fidelity. It is an adapted

version of the MBCT-Adherence Scale, which has been widely used to evaluate fidelity to the 8-week in-person MBCT protocol. The MBCT-T Adherence and Competence scale was developed by [name] and is pending publication. Adherence (Primary Outcome) is rated separately for: a) inclusion of formal components (e.g., homework assigned, guided exercise, inquiry, etc.) and b) teaching goals (e.g., learning to place and hold attention, recognizing aversion, etc.) for each session on a 0-3 scale. Competence (Secondary Outcome) is the ability to cultivate a therapeutic group-based learning environment and capacity to embody mindfulness skills and is rated separately on a scale of 0-3. Minimal expected fidelity in order to be considered "faithful" is an average score across sessions of  $\geq$  2.5 for

both adherence and competence.

Name: Treatment Session Adherence

Type: Primary Time Frame: Intervention

Brief Description: Treatment Session Adherence is a measure of treatment feasibility. The number of

MBCT-T treatment sessions attended will be recorded and software will record the number of EUC education modules read by each participant. A treatment arm will be considered feasible if participants attended/read 75% of sessions on average.

Name: Fidelity Checklist Type: Secondary Intervention

Brief Description: The checklists cover the rundown and activities of each mindfulness session based

on content within the treatments.

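### Aim 1B never tests MBCT within a site: sites are judged over all three arms and arms over all sites, so MBCT can miss its attendance or CSQ-8 benchmark at a site that passes

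*Combined protocol and SAP*

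**What the plan says.** The hypothesis is in section 3 (Aim 1B) and is repeated in section 9.1: "MBCT-T, MBCT-V, and EUC will be feasible (Primary Outcome: 75% Session Attendance) and acceptable". The sentence ends by placing this at each site.

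Section 9.1, Aim 1B, then gives two kinds of pass rule.

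- **Sites, averaged over arms.** "A site will be considered to demonstrate adequate feasibility if on average participants attended 75% of sessions across treatment arms at the site". For satisfaction, "A site will be considered to demonstrate adequate acceptability if on average participants report CSQ-8 scores > 24 across treatment arms at the site".
- **Arms, averaged over sites.** "A treatment arm will be considered feasible if on average participants attended 75% of sessions, across all sites". For satisfaction, "A treatment arm will be considered acceptable if CSQ-8 scores are > 24, across all sites".

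EUC is part of the site average: "Feasibility is assessed using Treatment Session Adherence (n = 144), which will be summed to indicate the number of treatment sessions attended", and 144 is the whole trial. For EUC, section 7.2.1.6 counts the "number of EUC education modules read by each participant", and section 7.2.1.3.2 says that engagement with each "module happens individually (not in a group) and will be tracked electronically by the secure hosting website". Summary statistics are promised by arm and by site. The arm-by-site cells are not mentioned.

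Elsewhere the plan keeps MBCT and EUC apart. Site fidelity under Aim 1A uses MBCT sessions only (32 per site). The Aim 2 decision rules set benchmarks that MBCT-T and MBCT-V must meet by arm and by site, and give EUC its own benchmarks and its own consequence.

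**The concern.** The hypothesis concerns each arm at each site, but the rules examine only the two margins of that three-by-three table. The Aim 2 requirement that the MBCT arms meet benchmarks by site therefore has no MBCT-only site figure behind it for attendance or CSQ-8.

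The quantities averaged also differ in kind: joining a weekly one-hour group session, and reading a module alone online. One third of a site's score comes from the second, and it says little about how well that site's patients attend or like MBCT.

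The site results feed the judgement on which sites, with what resources, go into Phase III. The error can run either way. A good EUC result can cover an MBCT shortfall, and a poor one can flag a site where MBCT does well.

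**Working it through.** **Inputs.** Allocation is 1:1:1 with 16 per arm per site (section 5.6; sample size paragraph for Aim 1), so each site mean weights the three arms equally and each arm mean weights the three sites equally. There are eight sessions or modules, so 75% is six. The benchmarks are 75% attendance and CSQ-8 above 24, on a scale of 8 to 32. No expected EUC attendance or EUC CSQ-8 is given, so the EUC values below are assumptions shown over a range.

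The plan's own figure for Aim 1B, power above .89, cannot be reproduced because its means, SDs and n are not printed. Nothing here depends on it.

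**Step 1: lowest MBCT mean at which a site passes.** With EUC mean E and MBCT mean m, the site mean is (2m + E)/3.

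- Attendance: m = (3 × 75 − E)/2.
- CSQ-8: m must exceed (3 × 24 − E)/2.

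**Step 2: what the other two sites need for the MBCT arm means to pass.** They must average (3 × 75 − m)/2 for attendance, and more than (3 × 24 − m)/2 for CSQ-8.

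| Outcome | Assumed EUC mean at the site | Site passes with MBCT mean down to | MBCT mean needed at the other two sites |
|---|---|---|---|
| Attendance | 80% | 72.5% | 76.25% |
| Attendance | 90% | 67.5% | 78.75% |
| Attendance | 95% | 65% | 80% |
| Attendance | 100% | 62.5% | 81.25% |
| CSQ-8 | 28 | just above 22 | above 25 |
| CSQ-8 | 30 | just above 21 | above 25.5 |
| CSQ-8 | 32 | just above 20 | above 26 |

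**Step 3: complete examples (MBCT-T, MBCT-V, EUC).**

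- Attendance: Site 1 = 65, 65, 95; Sites 2 and 3 = 82, 82, 90. The site means are 225/3 = 75.0 and 254/3 = 84.7 (twice). Each MBCT arm mean is (65 + 82 + 82)/3 = 76.3, and EUC is 275/3 = 91.7. Every benchmark passes, although both MBCT arms at Site 1 are 10 points short.
- CSQ-8: Site 1 = 22, 22, 29; Sites 2 and 3 = 26, 26, 28. The site means are 73/3 = 24.3 and 80/3 = 26.7 (twice). Each MBCT arm mean is 74/3 = 24.7, and EUC is 85/3 = 28.3. All pass.
- The reverse: MBCT at 84% and EUC at 55% gives (84 + 84 + 55)/3 = 74.3%, and the site misses.

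**Step 4: does scoring missing CSQ-8 as 8 close the gap?** Not necessarily. With completers at 28 throughout, 25% missing in MBCT gives 0.75 × 28 + 0.25 × 8 = 23, and 5% missing in EUC gives 0.95 × 28 + 0.05 × 8 = 27. The site mean is (23 + 23 + 27)/3 = 24.3, which passes.

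**Step 5: how often, allowing for chance.** This is an illustrative simulation of 20,000 sites with 32 MBCT and 16 EUC participants, beta-binomial attendance over eight sessions, an assumed within-person correlation of 0.3 and no group clustering. True MBCT attendance is 65%.

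| True EUC attendance | Pass, three-arm rule | Pass, MBCT-only rule |
|---|---|---|
| 75% | 6% | 3% |
| 85% | 21% | 3% |
| 90% | 34% | 3% |
| 95% | 52% | 3% |

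**The case against.** **The consequence is not automatic.** A reader might infer that the site average decides whether a site stays. It does not. Under the Aim 2 decision rules a missed site threshold leads to an inquiry into whether the barrier can be changed, and only then to considering removal. The plan also intends to monitor sites during the trial and to weigh feasibility information more broadly. This stands. But none of it supplies an MBCT threshold within a site, and a site that passes triggers no inquiry.

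**Gross failure would show.** A reader might infer that a site could fail to deliver MBCT altogether and still pass. It could not. Below 62.5% mean MBCT attendance, or at a mean MBCT CSQ-8 of 20 or less, even a perfect EUC result cannot lift the site over the line. Site fidelity is also an MBCT-only check, though it measures neither attendance nor satisfaction.

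**Nothing shows that EUC will score high.** A reader might infer that EUC is self-paced and easy to complete. The documents say that modules are released weekly, in step with the MBCT arms, and give no expected rate. At 75% EUC attendance there is no masking of the mean at all. This also stands, and it is why the size is given as a range.

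**The wording may be loose.** The plan sometimes uses across to mean for each. If the arm rules meant every site separately, the gap would close. However, the rules speak of averages and Aim 2 says its decision data are pooled across sites, so the pooled reading is the natural one. The text would need correcting on either reading.

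**Pooling has a purpose.** Aim 2 pools across sites to limit multiple comparisons and discrepant findings. That is a fair reason for the arm decisions. It is not a reason to mix EUC into a site's MBCT result.

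**Conclusion.** The concern holds as a mismatch between hypothesis and pass rule. H1 of Aim 1B is stated for each arm at each site, and no rule examines MBCT within a site on attendance or CSQ-8. Both margins can pass while MBCT at one site misses its benchmark, and a site can miss because of EUC alone.

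The size is moderate and bounded. The hidden shortfall is up to 2.5 points of attendance if EUC is at 80% and up to 12.5 points if EUC is at 100%. On CSQ-8, the MBCT mean can be as low as just above 22 to 20 when EUC averages 28 to 32. These figures assume equal arm sizes and the EUC values named. They show what the rule permits, not what is expected to happen. The matter is worth correcting before analysis because it affects what the pilot can say about its sites. It does not invalidate the trial.

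**What to change.** In section 9.1, Aim 1B:

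- At each site, apply the 75% attendance and CSQ-8 > 24 benchmarks separately to MBCT participants (n = 32) and to EUC participants (n = 16).
- Report all nine arm-by-site cells (n = 16 each). Pooling MBCT-T with MBCT-V can still hide one weak arm: 55% and 95% average 75%.
- Keep the three-arm site mean as descriptive only.
- In Aim 2, use the MBCT result for the site part of the MBCT benchmark and the EUC result for the EUC benchmark.
- Align H1 with the level at which it will be judged, and replace across where for each is meant.

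No new data are needed, only wording and table rows. The cost is precision. Relative to 48 participants, the standard error rises by a factor of √(48/32) = 1.22 for MBCT and √(48/16) = 1.73 for EUC, if variances are equal and clustering is ignored. The MBCT loss may be larger, because those participants sit in about four treatment groups per site. The cells of 16 are less precise still and should be read as descriptive.
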